3.3. Study Treatments

Participants will receive a single, sequential infusion of VRC07-523LS and CAP256V2LS in combination with a total of 10 VES doses received every 2 weeks during Periods 1 and 2. Participants will receive the first dose of VES alone and VRC07-523LS and CAP256V2LS will be administered 1 week later. Participants will continue their prescribed ART regimen during Period 1, and may restart ART in Period 4A, upon conclusion of Period 3 or if the ART restart criteria are met during Periods 2, 3, and 4B.

3.4. Duration of Treatment

Participants will receive study drugs, VRC07-523LS, CAP256V2LS, and VES, for a maximum of 18 weeks during Periods 1 and 2. Participants who have remained virologically suppressed (plasma HIV-1 RNA $<$ 50 copies/mL) or have not met the ART restart criteria by the end of Period 3 (maximum 43 weeks ATI [Periods 2 and 3]) will continue in either Period 4A and restart ART for 12 weeks, or Period 4B and remain off ART for a 12-week ATI extension.

3.5. Protocol-specific Discontinuation Criteria

- Intercurrent illness, unacceptable toxicity, or toxicity that would, in the judgment of the investigator, affect assessments of clinical status to a significant degree and/or compromises the participant's ability to continue in the study or is considered to not be in the participant's best interest
- Participant request to discontinue for any reason
- Participant noncompliance
- Discontinuation of the study at the request of Gilead Sciences (Gilead), a regulatory agency, or an institutional review board (IRB) or independent ethics committee (IEC)

3.6. End of Study

The end of study will be the last participant's last observation (or visit).

3.7. Poststudy Care

After a participant has completed/terminated their participation in the study, long-term care for the participants will remain the responsibility of their primary treating physician.

3.8. Source Data

The source data for this study will be obtained from participants clinical/hospital records, interactive web response system (IWRS), central laboratory, local laboratory, and specialty laboratory.

3.9. Biomarker Testing

3.9.1. Biomarker Samples to Address the Study Objectives

The following biological specimens will be collected from all participants who have provided consent to participate in this study and may be used to evaluate the association of systemic and/or tissue-based biomarkers with study drug response (including efficacy and/or AEs) and dosage selection, and to better understand the biological pathways, biology of HIV or related diseases, and/or the validation of a companion diagnostic for HIV cure. Because biomarker science is a rapidly evolving area of investigation, and AEs in particular are difficult to predict, it may not be possible to specify prospectively all tests that may be done on the specimens provided. The specific analyses will include but may not be limited to the biomarkers and assays listed below. The testing outlined below is based upon the current state of scientific knowledge. It may be modified during or after the end of study to remove tests no longer indicated and/or to add new tests based upon new state of the art knowledge.

Samples will be collected to measure biomarkers that may include but will not be limited to:

Blood specimens will be collected (> 1 time) at prebaseline/Day -13, baseline, 1-day and 7-day after VES, at various time points during the study (please see [Appendix 2](#), Study Procedures Table), end-of-Period 3 visit, and at the end-of-study visit for the isolation of PBMCs and plasma/serum for analyzing immune cell activation/phenotype, HIV-specific T cell responses, soluble protein (cytokines, chemokines, and inflammatory markers), CD4+ and CD8+ T cell absolute count, percentage, and CD4/CD8 ratio, and HIV-specific antibody profiling. Blood samples will be collected at prebaseline/Day -13 to evaluate soluble proteins in the TruCulture® Whole Blood Culture System.

From participants who provide additional consent, lymph node and GALT biopsies will be taken for some or all of the following tests: immunophenotyping, viral reservoir measurements, gene expression analysis and glycosylation profile analysis (depending on viable cells isolated).

Samples collected for biomarker assessments will be destroyed no later than 15 years after the end of study or per country requirements.

CCI

4. PARTICIPANT POPULATION

4.1. Number of Participants and Participant Selection

Approximately 25 participants will be enrolled in the study.

4.1.1. Participant Replacement

Participants who discontinue before the end of study will not be replaced.

4.2. Inclusion Criteria

Participants must meet *all* of the following inclusion criteria to be eligible for participation in this study:

- 1) Females recruited from the FRESH acute HIV infection cohort
- 2) Age \geq 18 years
- 3) Plasma HIV-1 RNA levels < 50 copies/mL at the screening visit
- 4) On ART regimen for ≥ 12 consecutive months prior to the screening visit
 - a. The following agents are allowed as part of the current ART regimen: nucleoside reverse-transcriptase inhibitors, raltegravir, bictegravir, dolutegravir, and rilpivirine.
 - b. A change in ART regimen ≤ 45 days prior to the prebaseline/Day -13 visit for reasons other than virologic failure (eg, tolerability, simplification, drug-drug interaction profile) is allowed. If the participant's ART regimen is changed, a plasma HIV-1 RNA level < 50 copies/mL at the prebaseline/Day -13 visit will be required to confirm eligibility.
 - c. Availability of a fully active alternative ART regimen, in the opinion of the investigator, in the event of discontinuation of the current ART regimen with development of resistance
- 5) Have all the following laboratory values at the screening visit:
 - a. Hemoglobin ≥ 10.0 g/dL
 - b. White blood cells ≥ 2500 cells/ μ L
 - c. Platelets $\geq 125,000$ /mL
 - d. Absolute neutrophil counts ≥ 1000 cells/ μ L
 - e. CD4+ T cell count ≥ 500 cells/ μ L
 - f. ALT, AST, and bilirubin $\leq 2 \times$ upper limit of normal (ULN)
 - g. Creatinine clearance ≥ 60 mL/min using Cockcroft-Gault formula {[Cockcroft 1976](#)}
- 1) Female Estimated Creatinine Clearance = $[(140 - \text{age in years}) \times (\text{weight in kg})]/[72 \times (\text{serum creatinine in mg/dL})] \times 0.85$
- 6) Women of childbearing potential to have documentation of agreement to follow study contraceptive requirements as outlined in [Appendix 5](#)

- 7) Documented plasma HIV-1 RNA viral load must be < 50 copies/mL for 12 consecutive months prior to screening:
 - a. ≤ 2 detectable HIV-1 RNA measurements that must be ≤ 1000 copies/mL at nonconsecutive visits within 12 months are acceptable
 - b. Determinations below the level of quantitation will be considered as detectable at the assay's threshold level
- 8) In the judgment of the investigator, be in good general health, based on review of the results from a screening visit (to include physical examination, measurement of vital signs, resting 12-lead electrocardiogram [ECG] and routine clinical laboratory testing), performed no more than 28 days prior to study drug administration
- 9) Must be willing and able to comply with all study requirements and available to complete the study schedule of assessments
- 10) Documented history of viral sensitivity to VRC07-523LS or CAP256V2LS at the screening visit

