6.9.1. Criteria for Discontinuation of Study Drug

Study drug may be discontinued in the following instances:

- Intercurrent illness that would, in the judgment of the investigator, affect assessments of clinical status to a significant degree. Following resolution of intercurrent illness, the participant may resume study dosing at the discretion of the investigator
- Unacceptable toxicity, or toxicity that, in the judgment of the investigator, compromises the ability to continue study-specific procedures or is considered to not be in the participant's best interest
- Participant request to discontinue for any reason
- Participant noncompliance
- Pregnancy during the study; refer to [Appendix 5](#)

- Discontinuation of the study at the request of Gilead, a regulatory agency or an IRB or IEC
- Participant receives study drug(s) and experiences 1 or more AE or laboratory abnormality as follows:
 - \geq Grade 3 treatment-emergent AE (including new finding of splenomegaly, mucosal petechiae or purpura on physical examination or CRS) judged by the investigator as at least possibly related to study drug, OR
 - \geq Grade 3 confirmed laboratory abnormality (including a confirmed significant drop in platelets to $< 50,000/\text{mm}^3$ and/or confirmed drop of 50% from baseline), unless there is a clear and obvious physiologic explanation for the events (eg, blood in urine occurring in a menstruating female, CK elevation after strenuous exercise, or triglyceride elevation that is nonfasting) judged by the investigators as at least possibly related to study drug, OR
 - A persistent (≥ 72 hours) \geq Grade 2 pyrexia considered related to study drug by the investigator, OR
 - Any SAE considered at least possibly related to study drug

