7.1.2.1. Protocol-Specific Serious Adverse Event Definitions

Protocol-specific SAEs: In this study, thrombocytopenia < 50,000 platelets will be considered medically important and therefore “serious.”

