Appendix 4. Gilead Grading Scale for Severity of Adverse Events and Laboratory Abnormalities

Antiviral Toxicity Grading Scale, Version 01 April 2015

HEMATOLOGY				
	Grade 1	Grade 2	Grade 3	Grade 4
Hemoglobin				
HIV POSITIVE	8.5 to 10.0 g/dL	7.5 to < 8.5 g/dL	6.5 to < 7.5 g/dL	< 6.5 g/dL
Adult and Pediatric \geq 57 Days	85 to 100 g/L	75 to < 85 g/L	65 to < 75 g/L	< 65 g/L
HIV NEGATIVE	10.0 to 10.9 g/dL	9.0 to < 10.0 g/dL	7.0 to < 9.0 g/dL	< 7.0 g/dL
Adult and Pediatric \geq 57 days	100 to 109 g/L OR Any decrease from Baseline	90 to < 100 g/L OR Any decrease from Baseline	70 to < 90 g/L OR Any decrease from Baseline	< 70 g/L
Infant, 36–56 Days (HIV POSITIVE OR NEGATIVE)	2.5 to < 3.5 g/dL 25 to < 35 g/L	3.5 to < 4.5 g/dL 35 to < 45 g/L	\geq 4.5 g/dL \geq 45 g/L	
Infant, 22–35 Days (HIV POSITIVE OR NEGATIVE)	8.5 to 9.4 g/dL 85 to 94 g/L	7.0 to < 8.5 g/dL 70 to < 85 g/L	6.0 to < 7.0 g/dL 60 to < 70 g/L	< 6.0 g/dL < 60 g/L
Infant, 1–21 Days (HIV POSITIVE OR NEGATIVE)	9.5 to 10.5 g/dL 95 to 105 g/L	8.0 to < 9.5 g/dL 80 to < 95 g/L	7.0 to < 8.0 g/dL 70 to < 80 g/L	< 7.0 g/dL < 70 g/L
Absolute Neutrophil Count	1000 to 1300/mm ³	750 to < 1000/mm ³	500 to < 750/mm ³	< 500/mm ³
Adult and Pediatric, \geq 7 Months^a	1.00 to 1.30 GI/L	0.75 to < 1.00 GI/L	0.50 to < 0.75 GI/L	< 0.50 GI/L
Absolute CD4+ Count				
HIV NEGATIVE ONLY	300 to 400/mm ³	200 to < 300/mm ³	100 to < 200/mm ³	< 100/mm ³
Adult and Pediatric $>$ 13 Years	300 to 400/ μ L	200 to < 300/ μ L	100 to < 200/ μ L	< 100/ μ L
Absolute Lymphocyte Count				
HIV NEGATIVE ONLY	600 to 650/mm ³	500 to < 600/mm ³	350 to < 500/mm ³	< 350/mm ³
Adult and Pediatric $>$ 13 Years	0.60 to 0.65 GI/L	0.50 to < 0.60 GI/L	0.35 to < 0.50 GI/L	< 0.35 GI/L
Platelets	100,000 to < 125,000/mm ³ 100 to < 125 GI/L	50,000 to < 100,000/mm ³ 50 to < 100 GI/L	25,000 to < 50,000/mm ³ 25 to < 50 GI/L	< 25,000/mm ³ < 25 GI/L

HEMATOLOGY

	Grade 1	Grade 2	Grade 3	Grade 4
White Blood Cells	2000/mm ³ to 2500/mm ³	1,500 to < 2,000/mm ³	1000 to < 1,500/mm ³	< 1000/mm ³
	2.00 GI/L to 2.50 GI/L	1.50 to < 2.00 GI/L	1.00 to < 1.50 GI/L	< 1.00 GI/L
Hypofibrinogenemia	100 to 200 mg/dL	75 to < 100 mg/dL	50 to < 75 mg/dL	< 50 mg/dL
	1.00 to 2.00 g/L	0.75 to < 1.00 g/L	0.50 to < 0.75 g/L	< 0.50 g/L
Hyperfibrinogenemia	> ULN to 600 mg/dL	> 600 mg/dL	—	—
	> ULN to 6.0 g/L	> 6.0 g/L	—	—
Fibrin Split Product	20 to 40 µg/mL	> 40 to 50 µg/mL	> 50 to 60 µg/mL	> 60 µg/mL

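### The platelet entry limit in criterion 5c and the synopsis is written per mL, 1000-fold off the per mm³ scale the protocol uses for platelets elsewhere

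*Protocol*

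**What the plan says.** Criterion 5 in protocol Section 4.2 lists laboratory values required at screening. Item 5c reads "Platelets $\geq 125,000$ /mL", and the synopsis gives the same number and unit. The neighbouring cell counts use a different volume: item 5b is "White blood cells ≥ 2500 cells/ μ L", and the neutrophil and CD4+ limits are also per microlitre.

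Platelets appear with a unit in four other places, always per mm³:

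- Appendix 4 sets Grade 1 at "100,000 to < 125,000/mm ³ 100 to < 125 GI/L" and Grade 4 at "< 25,000/mm ³ < 25 GI/L".
- Section 6.9.1 names, among the laboratory abnormalities that may lead to stopping study drug, a "confirmed significant drop in platelets to $< 50,000/\text{mm}^3".
- Appendix 3 repeats the 50,000/mm³ figure as a Grade 3 or 4 abnormality.
- Section 1.2.5.2 reports a count of 122,000/mm³ in an earlier study and calls it Grade 1.

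Section 7.1.2.1 gives a protocol-specific serious adverse event threshold with no unit: "thrombocytopenia < 50,000 platelets will be considered medically important".

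**The concern.** An entry limit is a decision threshold, and 5c is the only numeric platelet limit for entry. Platelets also get special attention in this protocol. Section 1.5 lists thrombocytopenia among the nonclinical findings for vesatolimod, Section 6.9.1 names platelets in the discontinuation criteria, and Section 7.1.2.1 gives them their own seriousness rule.

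Two analyses use the same information. SAP Section 4.3 counts enrolled participants who failed specific eligibility criteria. If 5c is applied literally, a participant with a low platelet count would almost never be counted there. SAP Section 7.2.2.1 calls a laboratory value treatment-emergent only if it is at least one grade worse than baseline. A participant who entered with Grade 4 platelets could not show a treatment-emergent platelet decrease, and graded laboratory abnormalities are a primary endpoint. This second consequence is hypothetical, because it needs such a participant to have been enrolled.

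**Working it through.** **Inputs**

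| Quantity | Value | Source |
|---|---|---|
| Entry limit as written | 125,000 per mL | Protocol 4.2 (5c); synopsis |
| Grade 1 platelets | 100,000 to < 125,000 per mm³ | Appendix 4 |
| Grade 3 platelets | 25,000 to < 50,000 per mm³ | Appendix 4 |
| Grade 4 platelets | < 25,000 per mm³ | Appendix 4 |
| Discontinuation level | < 50,000 per mm³ | Sections 6.9.1, Appendix 3 |

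**Is the protocol's per mm³ scale consistent with itself?** Yes. Appendix 3 calls counts below 50,000/mm³ Grade 3 or 4, and Grade 3 in Appendix 4 begins below 50,000/mm³. The 122,000/mm³ called Grade 1 in Section 1.2.5.2 lies inside the Grade 1 band. The entry limit is the figure that does not fit.

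**Conversion.** 1 mL = 1000 mm³ = 1000 µL, so count per mm³ = count per mL ÷ 1000.

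- Entry limit: 125,000 ÷ 1000 = 125/mm³.
- Appendix 4 equates 100,000/mm³ with 100 GI/L, so 125/mm³ = 125 ÷ 1000 = 0.125 GI/L. That value is itself Grade 4.

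**Distance from the protocol's own thresholds**

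- Same number read per mm³: 125,000 ÷ 125 = 1000-fold.
- Discontinuation level: 50,000 ÷ 125 = 400 times the written limit.
- Grade 4 boundary: 25,000 ÷ 125 = 200 times the written limit.

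**What passes 5c as written**

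| Count per mm³ | Count per mL | At or above 125,000/mL? | Appendix 4 grade |
|---|---|---|---|
| 130 | 130,000 | Yes | 4 |
| 5,000 | 5,000,000 | Yes | 4 |
| 24,999 | 24,999,000 | Yes | 4 |
| 49,999 | 49,999,000 | Yes | 3 |

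Only counts below 125/mm³ fail.

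**Comparison reading.** If the same number is read per mm³, 125,000 is exactly where Grade 1 ends, and entry would require Grade 0 platelets. This coincidence suggests a unit slip. It does not replace a statement from the sponsor of what was meant.

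**The case against.** The strongest reply is that 5c never acts alone. All inclusion criteria must be met and no exclusion criterion may apply. Exclusion 11d bars a past or present platelet disorder, including thrombocytopenia without an explanation. Inclusion 8 asks the investigator to judge general health from the screening results, routine laboratory tests included. Exclusion 13 covers serious or active haematological illness. A reader might infer from the arithmetic that the trial as written admits participants with Grade 4 thrombocytopenia. The documents do not support that, because these three criteria would probably stop most such participants. They do not remove the point, since they rest on history and judgement and none contains a platelet number.

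A reader might also infer that 5c excludes no one, or that eligibility checks built on it could never fire. The first is not literally true, because counts below 125/mm³ fail. The second has no basis, because neither document describes an automated platelet check. A clinician would probably see the intended reading at once, given the match with the Grade 1 limit.

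A lost Greek letter in the PDF could turn µL into mL. The protocol does print the Fc gamma receptor abbreviation both with the Greek letter and with a plain g. But the white cell, neutrophil and CD4+ limits beside the platelet line keep their micro sign in both the synopsis and Section 4.2. A symbol fault would have to hit the same single line twice and spare its neighbours. That is unlikely, though only the printed page can exclude it.

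The safety context should be stated in full. Section 1.5 also says that treatment-emergent platelet decreases were not seen at doses up to 12 mg in two studies in people with HIV, and that blood counts are monitored throughout.

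Finally, correcting the text cannot change who entered. SAP Section 2.1.2 describes the sentinel review in the past tense, and Section 2.3 treats the last participant's end-of-Period 3 visit as having taken place. That stands. It makes checking what was done at screening more useful than the wording change alone.

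**Conclusion.** The platelet entry limit is wrong as written in two places. It is 1000-fold off the per mm³ scale used in Section 6.9.1, Appendix 3 and Appendix 4, and 200 times below the Grade 4 boundary. Taken alone, it screens out practically no one. The practical risk is smaller than these factors suggest, because inclusion 8 and exclusions 11d and 13 also apply.

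The conclusion assumes that the unit in the PDF text is the unit on the page. It does not extend to any claim that a participant with severe thrombocytopenia was enrolled or that a primary endpoint is biased, as the documents hold no evidence of either. Sample size, analysis sets, grading rules and stopping rules are unaffected.

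The missing unit in Section 7.1.2.1 is editorial. It contradicts nothing, since the same number appears with its unit in Section 6.9.1 and Appendix 3.

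**What to change.** 1. Check the printed page, then reconcile the platelet unit in the synopsis and in Section 4.2 (5c) with Section 6.9.1, Appendix 3 and Appendix 4. The sponsor should state which limit was meant.
2. Confirm from site and laboratory records which unit was applied at screening, and compare each enrolled participant's screening platelet count with the reconciled limit.
3. Use the reconciled unit when tabulating eligibility deviations under SAP Section 4.3, and say so in a footnote to that table and in the study report.
4. As a tidy-up only, add the unit to the threshold in Section 7.1.2.1.

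The cost is a unit in two places, an editorial addition in a third, and a review of about 25 screening records at most. No visit, sample, endpoint or analysis method changes.

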4.3. Exclusion Criteria

Participants who meet *any* of the following exclusion criteria are not eligible to be enrolled in this study:

- 1) Positive serum pregnancy test
- 2) Nursing females
- 3) Participants with coinfection and/or immunosuppression as described below:
 - a. Autoimmune disease requiring ongoing immunosuppression (except in the case of mild autoimmune disease that only requires topical treatments)
 - b. Evidence of chronic HBV infection (defined as positive HBsAg OR positive hepatitis B core antibody and negative hepatitis B surface antibody)
 - c. Evidence of current HCV infection (defined as positive hepatitis C antibody and HCV RNA > lower limit of quantitation [LLOQ])
 - positive anti-HCV antibody and negative HCV polymerase chain reaction results are acceptable
 - d. Documented history of pre-ART CD4+ T cell count nadir < 200 cells/ μ L (unknown pre-ART CD4+ T cell count nadir is acceptable)
 - e. History of opportunistic illness indicative of Stage 3 HIV as referenced in [Appendix 6](#)
 - f. Acute febrile illness within 4 weeks prior to the first dose
- 4) Have current alcohol or substance abuse judged by the investigator to potentially interfere with participant's compliance or participant's safety
- 5) Have poor venous access that limits phlebotomy

- 6) Have been treated with systemic steroids, immunosuppressant therapies, or chemotherapeutic agents within 3 months prior to screening or are expected to receive these agents during the study (eg, corticosteroids, immunoglobulins, and other immune- or cytokine-based therapies)
- 7) Have previous or current receipt of humanized or human mAbs, or polyclonal immunoglobulin
- 8) Have previous history of an antidrug antibodies response to a therapeutic agent
- 9) Have previous receipt of an HIV vaccine
- 10) Received any vaccine or immunomodulatory medication within 4 weeks prior to screening. Elective vaccination (eg, flu shot, hepatitis A or B vaccine) during the course of the study will require prior approval from the sponsor
 - a. COVID-19 vaccinations are allowed, with the requirement that they should not be administered within 5 days of receiving IMP
- 11) Have a history of any of the following:
 - a. Significant serious skin disease, such as but not limited to rash, food allergy, eczema, psoriasis, or urticaria
 - b. Significant drug sensitivity or drug allergy (such as anaphylaxis or hepatotoxicity). Any history of anaphylaxis and related symptoms such as hives, respiratory difficulty, or angioedema
 - c. Known hypersensitivity to the study drugs, metabolites, or formulation excipients
 - d. Previous or current history of bleeding disorder, platelet disorder including unexplained acute or chronic thrombocytopenia
 - e. Autoimmune diseases including type 1 diabetes mellitus
- 12) Have current Class C AIDS-defining condition
- 13) Have any serious or active medical or psychiatric illness (including depression) that, in the opinion of the investigator, would interfere with participants treatment, assessment, or compliance with the protocol. This would include renal, cardiac, hematological, hepatic, pulmonary (including chronic asthma), endocrine (including diabetes), central nervous, gastrointestinal (including an ulcer), vascular, metabolic (thyroid disorders, adrenal disease), immunodeficiency disorders other than HIV-1 infection, active infection, or malignancy that are clinically significant or requiring treatment
- 14) Participation in any other clinical study (including observation studies) without prior approval from the sponsor is prohibited while participating in this study

5. INVESTIGATIONAL MEDICINAL PRODUCTS

5.1. Treatment Assignment

It is the responsibility of the investigator to ensure that the participants are eligible for the study prior to enrollment. Participants will be assigned a screening number at the time of consent.

Treatment assignment in the interactive voice/web response system will be performed in clinic at the baseline/Day 0 visit, provided that all other screening procedures have been completed and participant eligibility has been confirmed. If a participant's ART regimen is changed ≤ 45 days prior to prebaseline/Day -13, plasma HIV-1 RNA < 50 copies/mL at prebaseline/Day -13 visit is required to confirm eligibility. Once a participant number has been assigned, it will not be reassigned to any other participant.

